3.2 Secondary objectives

- Evaluate the efficiency of the Lit-control® pH Meter device and the Lit-control®pH Down food supplement in the pH control.
- Determine the safety of the food supplement Lit-control®pH Down.
- Evaluate compliance / adherence with the measures for the determination and control of pH recommended by the doctor.
- Know the cost-effective profile of the intervention (from the moment of placing the double J stent to its withdrawal).

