7.2 Secondary valuation variables

- Sociodemographic and anthropometric variables (sex, age, weight, height, BMI, marital status, work situation, toxic habits).
- Family history of obstructive uropathies.
- Personal clinical history of interest (previous nephritic colic, kidney transplant, acute pathology of interest, chronic pathology (HBP, Chronic Kidney Disease, Diabetes and others).

- Anatomical alterations in the urinary system.
- Previous incidence of obstructive uropathy (urolithiasis, stenosis and ureteral injuries, retroperitoneal fibrosis).
- Previous need for stent (indwelling stent reason, date of stent placement and removal, type of stent and symptoms (if any) associated with it)
- Date of placement and removal of the double J stent (current) and Total time with double J stent until its withdrawal (days).
- Total pH control time (days).
- Urine analysis of 2 hours in basal fasting (volume of urine, pH, creatinine, uric acid).
- Urine culture (infection: yes / no).
- Complications observed due to placement or permanence of the stent and symptoms associated with indwelling stent.
- Image of the stent (scanner or X-ray).
- Adherence to treatment / recommendations of the doctor.
- Adverse events attributable to the treatment or study recommendations.
- Data on stent removal (date, complications, type of procedure and duration of extraction).
- Satisfaction of the researcher with preventive therapy.
- Patient satisfaction with preventive therapy.
- Pharmacoconomic data (direct costs): stent placement intervention, consultation visits, emergency visits, hospitalizations, medication administered, intervention (cost and type) for stent removal and total direct cost of the patient during the study (estimated at from the data provided by the center).

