7.4 End points

- Profile / Characteristics of the patient to whom a double J stent is placed.
- Comparison between groups of the results of the stent study (type and size of the crystals formed and degree of global calcification of each end).
- Success rate in pH control below 6.2 during the study.

- Percentage of stent extractions in the first attempt.
- Rate of complications in the extraction of the stent.
- Rate of adverse events attributable to treatment.
- Percentage of patients compliant (adherence > 80%) of the study interventions at 8 weeks (final visit).
- Degree of satisfaction of the researcher with the results of pH control.
- Degree of patient satisfaction with the use of the products under study.
- Cost-effectiveness of the intervention object of study according to the direct costs observed.

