9.6.2 Security Reports

The promoter must be informed immediately of all serious adverse events, except those that are specified in the protocol or other document. It will be reported quickly, in writing, in detail and in the time periods specified by the promoter in the protocol. These follow-up reports must identify the subjects by means of the codes assigned in the CB and not by the names of the subjects, personal identification numbers and / or addresses.

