11 ADVERSE EVENTS

The Adverse Events (AA) produced during the study will be evaluated. An AA is defined as any harmful event in a patient after randomization and during the performance of a study, even if it is considered not to be related to the treatment of the study. In this CE, the AAs in the CRD will be collected and recorded, as long as they are serious (if they cause clinical signs or symptoms and are considered clinically significant).

Diseases or medical conditions that were present before administering the product under study, will only be considered as AA if there is a worsening after the start of the study intervention (any procedure specified in the protocol).

To the extent possible, AAs will be described based on:

- Duration (start and end dates).

- Degree of severity (mild, moderate, severe).
- Relationship with the study medication (suspected / not suspected).
- Action (s) taken to correct it.

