11.2 Serious Adverse Events

Information on Serious Adverse Events (AAG) and Unexpected Serious Adverse Reactions (RAGI) with suspected causal relationship with the treatments under study, will be collected and recorded in the notification form of Serious Adverse Events (RD223 / 2004). Such serious adverse events must also be notified to the AEMPS, which will be done from the ESIC and for this the investigator must notify it within 24 hours of its knowledge. Only serious, unexpected AAs related to the treatments under study will be reported to the AEMPS.

AAG or RAGI is considered any adverse event or adverse reaction at any dose:

- Produce death of patients,
- Threatens the subject's life,
- Make necessary the hospitalization of the subject or the prolongation of it,
- Produces disability or permanent or significant disability, or
- Lead to an abnormality or congenital malformation.

The intensity of AA will be classified as mild, moderate or severe. The researcher will record the relationship of the study product with the AA according to the following causality terms:

- Related: the AA follows a reasonable time sequence from the moment of exposure to the product. It can not be explained by the clinical condition of the subject or by the procedures / conditions of the study. AA decreases after discontinuation of the study product and reappears once the study product is re-administered.
- Possibly related: the AA follows a reasonable temporal sequence from the moment of exposure to the product, but it may have been caused by the clinical condition of the subject or by the procedures / conditions of the study.
- Improbably related: the temporal association between the AA and the product of the study is such that it is unlikely that there is any reasonable relationship between them. The relationship is not likely due to other possible explanations.
- Not related: the AA, without a doubt, has been caused by the clinical condition of the subject or by the procedures / conditions of the EC. A reasonable explanation must be given, for example, that the product under investigation or an incompatible temporal relationship has not been consumed.

- Not evaluable: the report that indicates an adverse reaction can not be judged because the information that is counted is insufficient or contradictory, and no extra data can be added or the existing ones can be verified.

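### The only general adverse-event end point counts events judged attributable to treatment, with no stated cut-off, and the recording rules may prevent a comparison of all events by arm

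*Protocol*

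**What the plan says.** Section 3.2 sets an unrestricted secondary objective: "Determine the safety of the food supplement Lit-control®pH Down". Two places carry it into the data.

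- Section 7.4 has one general adverse-event end point: "Rate of adverse events attributable to treatment".
- Section 7.2 lists the matching variable as "Adverse events attributable to the treatment or study recommendations".

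Section 11 defines an adverse event more widely, as any harmful event after randomisation, "even if it is considered not to be related to the treatment of the study". The same section then narrows what is entered: "the AAs in the CRD will be collected and recorded, as long as they are serious". It explains serious there as causing signs or symptoms and being clinically significant.

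Causality appears on two scales. Section 11 has two levels, suspected or not suspected. Section 11.2 has five terms, recorded by the investigator: related, possibly related, improbably related, not related and not evaluable.

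On serious events, section 9.6.2 says "The promoter must be informed immediately of all serious adverse events", with an exception for those specified in the protocol or another document. Section 11.2 says that serious adverse events and unexpected serious reactions "with suspected causal relationship with the treatments under study, will be collected and recorded".

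**The concern.** In a randomised, masked, placebo-controlled trial, the difference between arms in all events estimates what the supplement causes, without anyone having to decide the cause of a single event. The named end point gives this up and counts only events that an investigator attributes to treatment. An effect nobody expects, or one that resembles a stent symptom, is the kind most likely to be called unrelated and so drop out.

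The count also has no defined numerator. Nothing says which of the five terms amount to attributable, or how they map to suspected and not suspected. The choice matters because, in section 11.2, the term related requires the event to recur when the product is given again, and the protocol describes no such step. Few events could qualify, so the rate depends largely on whether possibly related counts.

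The recording rules add a second filter. If events enter the CRD only when serious, a comparison of all events cannot be recovered at the analysis stage.

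**Working it through.** **The plan's own figures.** The protocol states no adverse-event rate, safety hypothesis or safety power. Its only sample-size figures (section 6.8) concern the incrustation score, and they reproduce if a two-sided 5% level is assumed:

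- The two-sample t-test for effect size 0.6 and 80% power needs 44.59 per arm.
- Dividing by the Mann-Whitney efficiency 3/π gives 46.69, so 47 per arm and 94 in total.
- 94 / 0.9 = 104.4, rounded up to 105. With 1:1 allocation, 105 / 2 = 52.5, taken as 52 per arm.

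**What counts as an event, section by section.**

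| Section | Events covered |
|---|---|
| 11, definition | Any harmful event after randomisation, related or not |
| 11, recording | Only if serious, meaning symptomatic and clinically significant |
| 11.2, seriousness | Death, threat to life, hospitalisation, disability, congenital anomaly |
| 7.2 | Attributable to treatment or study recommendations |
| 7.4 | Attributable to treatment |

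The two meanings of serious differ, and the end point is narrower than the definition.

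**Effect of the filter on power.** All rates here are assumptions. Let b be the background risk in both arms and e the extra risk caused by treatment. Let s be the share of caused events called attributable, and f the share of background events called attributable.

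- All events: control b, treated 1 − (1 − b)(1 − e).
- Attributed events: control bf, treated 1 − (1 − bf)(1 − es).

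Take b = 10% and a treated risk of 30%, so e = 1 − 0.70/0.90 = 22.2%. Exact Fisher power, two-sided 5%, 52 per arm:

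| Events counted | Control | Treated | Power |
|---|---|---|---|
| All | 10% | 30% | 66.5% |
| Half, whatever the cause (each rate halved) | 5% | 15% | 26% |
| s = 0.9, f = 0.1 | 0.10 × 0.1 = 1% | 1 − 0.99 × 0.80 = 20.8% | 91% |
| s = 0.7, f = 0.2 | 0.10 × 0.2 = 2% | 1 − 0.98 × 0.844 = 17.2% | 67% |

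With s = f = 0.5 in the formula, instead of simple halving, the rates are 5% v 15.6% and the power is 29%.

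A higher background shows the same pattern. With b = 30%, e = 20% and 47 per arm, all events (30% v 44%) have 22% power. Accurate attribution (s = 0.9, f = 0.1; 3% v 20.5%) gives 67%, and uninformative attribution (s = f = 0.5; 15% v 23.5%) gives 12%.

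**Bias between arms.** Suppose both arms have a true rate of 20%, and 60% of events are attributed in one arm but 30% in the other. The result is 0.20 × 0.6 = 12% against 0.20 × 0.3 = 6%. Equal events would have to be judged differently by arm, which requires unmasking. Section 6.3.4 has adverse effects recorded at the final visit, where the patient also hands over the pH diary unless it was entered online. Since the supplement is meant to lower pH, this is a possible route. The protocol gives no evidence that it operates, or to what extent. Even 12% v 6% would reach p ≤ 0.05 in only 9% of trials at 52 per arm.

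**The case against.** The strongest reply is that attribution removes background noise. Patients with a stent have many symptoms unrelated to a capsule, and a masked investigator who sorts events well makes the comparison sharper. The calculation supports this: a reader might infer that the restricted end point loses power in general, and it does not. A reader might also infer a false excess in one arm, but coded boxes and matched packaging (section 10.2) protect against that, and the protocol does not show that masking fails.

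Secondly, a SAP that is not shown may tabulate all events and define attributable. Sections 8.1 and 8.2 already describe every CRD variable and test the qualitative ones. Stent complications, urine culture, hospitalisations and extraction complications are collected without any attribution. This weakens the point but does not remove it. Those items are not a comparison of all adverse events, the protocol itself fixes the end point, and a SAP cannot restore events that were never recorded.

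Thirdly, section 11.2 does not clearly restrict which serious events are collected. Its causal qualifier may attach only to unexpected serious reactions, and its last sentence on the subject concerns reporting to the agency. Section 9.6.2 governs notification of the sponsor and carries an exception. A flat contradiction between the two would be too strong a reading; the wording is ambiguous. These replies stand as limits on the point. The mismatch between end point and definition, the two causality scales and the recording rule remain.

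**Conclusion.** The point holds as a defect in how the safety end point is defined and how events are recorded. It should be corrected, but it does not touch the primary analysis. As written, the safety objective would be answered on a subset chosen by investigator judgement, with no cut-off and two scales, and the events left out may not be in the database. The main harm is that unexpected effects can be missed.

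The size cannot be given as one number, because the protocol states no event or attribution rates. Under the assumed 30% v 10% with 52 per arm, power moves from 66.5% to as little as 26% or as much as 91%, depending on how well causes are judged. Neither a general loss of power nor a bias between arms is established.

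**What to change.** 1. In section 7.4, make the safety end point the percentage of patients with any adverse event, and with any serious adverse event, by arm and regardless of causality. Change the variable in section 7.2 to match.
2. Keep attributed events as a supportive summary, on one causality scale, naming in advance which categories count as attributable.
3. Reconcile the recording rule in section 11 with that section's own definition of an adverse event, and its meaning of serious with the criteria in section 11.2. Without this step the first change cannot be carried out.
4. Reconcile sections 9.6.2 and 11.2 on which serious events are collected, as distinct from which are reported to the agency.

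The cost is modest: changes of wording, fuller event recording at the centres and one more table. More background stent-related events will appear in both arms, which can dilute a difference; the supportive summary of attributed events helps with that.

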8 STATISTICAL ANALYSIS

All data will be analyzed using the statistical package SPSS-Windows.

8.1 Descriptive statistics

A descriptive statistic of all the variables collected in the CRD will be made.

The categorical variables will be presented in the form of lists of frequencies and proportions. For the quantitative variables (continuous or ordinal), indices of central tendency (mean, median, mode) and dispersion (standard deviation and maximum and minimum values) will also be presented.

8.2 Objectives of the study

In order to analyze the differences between continuous qualitative variables between the experimental group and the control, the T-Student test will be used for two independent samples, in case the condition of normality can be accepted.

variables in each of the groups. Otherwise, we will proceed with its non-parametric counterpart: U-Mann-Whitney.

In the case of the qualitative variables included in the CRD, the test to be used will be Chi-Square or through Fisher's exact test (when the percentage of expected values less than 5 exceeds 20%).

The possibility of carrying out additional analyzes, depending on the results, with the relevant statistical tests in each case is not ruled out.

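### Section 8.2's normality rule would probably send total direct cost to Mann-Whitney, which does not test the mean cost difference that the cost-effectiveness end point needs

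*Protocol*

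**What the plan says.** Section 8.2 (Objectives of the study) has one rule for continuous variables compared between arms: "the T-Student test will be used for two independent samples, in case the condition of normality can be accepted". If it cannot be accepted, "Otherwise, we will proceed with its non-parametric counterpart: U-Mann-Whitney". The protocol calls these variables continuous qualitative. That must mean quantitative, because qualitative variables have their own paragraph with chi-square or Fisher's test. The section closes by leaving open further, unspecified analyses that depend on the results.

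Section 7.2 collects a "total direct cost of the patient during the study". Its components include "stent placement intervention, consultation visits, emergency visits, hospitalizations, medication administered" and the procedure for stent removal. Section 3.2 makes the cost-effectiveness profile, from stent placement to withdrawal, a secondary objective. Section 7.4 lists the end point "Cost-effectiveness of the intervention object of study according to the direct costs observed". For quantitative variables, section 8.1 promises "indices of central tendency (mean, median, mode) and dispersion (standard deviation and maximum and minimum values) will also be presented".

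No exception to the 8.2 rule and no separate method for costs is given anywhere in the protocol.

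**The concern.** A cost-effectiveness comparison rests on the difference in arithmetic mean cost, because the mean times the number of patients is the total spent. Mann-Whitney tests whether a patient in one arm tends to cost more than a patient in the other, that is, whether P(experimental > control) = 0.5. The two questions coincide in direction when the arms differ only by a shift. They can part when one arm has fewer very expensive patients but a small extra cost for everyone, a pattern that a preventive product can produce. An expensive hospitalisation then counts for little more than any other top rank, while the small extra cost moves every rank.

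At stake is how the cost result is read: a p-value on ranks beside a cost-effectiveness statement built on means. The p-value could miss a saving or, under some cost patterns, point the other way.

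**Working it through.** **1. Sample size, used only to set the number per arm.** The protocol gives no figure for the cost analysis. Section 6.8 gives 94 evaluable patients for an effect size of 0.6 and 80% power. Assuming two-sided alpha 0.05 (none is stated), the normal approximation gives 2 × (1.96 + 0.84)² / 0.6² = 43.6, so 44 per arm. Dividing by the Mann-Whitney efficiency 3/π gives 44 / 0.955 = 46.1, so 47 per arm and 94 in total. Allowing for 10% loss, 94 / 0.9 = 104.4, so 105. Both figures reproduce. The checks below use 47 per arm.

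**2. Which branch of the rule applies.** Non-normality is an expectation, not a statement in the protocol. With the cost model of step 3, a Shapiro-Wilk test rejected normality in at least one arm in over 99% of simulated trials.

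**3. Assumed cost model.** All cost figures are assumptions.
- Routine cost: normal, mean 1,500, SD 100, 200, 400 or 600.
- Expensive event: gamma (shape 2), mean 5,000, in 10% of controls and 4% of experimental patients.
- Supplement cost *s* added to every experimental patient: 100, 50 or 0. Zero is a live reading. Section 7.2 does not name the supplement among the costs, and the Annex 4 letter says that the sponsor supplies it free.

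True mean difference = *s* + 5,000 × (0.04 − 0.10) = *s* − 300, that is −200, −250 or −300. The experimental arm is cheaper in every case.

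**4. What Mann-Whitney sees.** Treat an event patient as always outranking a routine one (an approximation). The pairs are: both routine 0.96 × 0.90 = 0.864; event in the experimental patient only 0.04 × 0.90 = 0.036; event in the control only 0.96 × 0.10 = 0.096; both 0.004. Then

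P(exp > control) ≈ 0.864 × Φ(*s* / (SD√2)) + 0.036 + 0.004/2.

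- *s* = 100, SD 100: 0.864 × 0.760 + 0.038 = 0.695.
- *s* = 100, SD 600: 0.864 × 0.547 + 0.038 = 0.511.
- *s* = 0, any SD: 0.864 × 0.5 + 0.038 = 0.470.

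With *s* = 100 the ranks lean towards dearer although the mean is lower, strongly only if routine costs are uniform. With *s* = 0 they lean the right way, but weakly.

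**5. Simulation at 47 per arm: share of trials in which Mann-Whitney is significant with the experimental arm dearer.**

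| Supplement cost | True mean difference | SD 100 | SD 200 | SD 400 | SD 600 |
|---|---|---|---|---|---|
| 100 | −200 | 92% | 31% | 9% | 4.5% |
| 50 | −250 | 32% | 8% | 2% | 1% |
| 0 | −300 | under 1% | under 1% | under 1% | under 1% |

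Figures are approximate. In the last row, the true saving is flagged as significant in only about 7% of trials.

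**6. A second cost model.** Routine cost lognormal with mean 1,000 and log-SD 0.15; an event adding 6,000 in 15% v 5%; supplement cost 100. True difference = 100 + 6,000 × (0.05 − 0.15) = −500, yet P(exp > control) = 0.60. Mann-Whitney was significant in 39% of 20,000 trials, practically always towards dearer. With the true means made equal (events 15% v 13.3%), it rejected in 60%. This model also assumes that the supplement is costed and that routine costs are fairly uniform.

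**7. What a mean-based analysis could show.** For the step 3 model, the event variance per patient is p × 5,000² × 1.5 − (5,000p)²: 3.50 million for controls and 1.46 million for experimental patients. Adding 2 × 200² = 0.08 million for routine cost and dividing by 47 gives 5.04 million / 47 = 107,000, so a standard error of about 330. A 95% interval is then roughly ±1.96 × 330 ≈ ±650 around a true saving of 200 to 300. Welch's test was significant in about 5 to 12% of trials.

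**The case against.** The strongest reply is that section 8.2 is a generic test rule and never names costs. Cost-effectiveness joins cost and effect, and the protocol defines neither a ratio nor an effect measure, so the economic method may simply have been left to a later plan. Section 8.1 reports mean costs, so a mean difference can be formed whatever test is run. This stands in part. A reader might infer that the protocol names Mann-Whitney as its cost-effectiveness analysis; it does not. But total direct cost is a collected continuous variable, 8.2 is the section on the study objectives, and its rule has no exception. The descriptive means carry no planned inference, and an open clause for results-dependent analyses does not supply it. The point is therefore a stated rule that fits this variable badly, not an omission.

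A second reply is that reversal depends on costing the supplement and on uniform routine costs. This stands. Several centres, different removal procedures and stent times of 3 to 8 weeks could well give a larger spread than SD 100 or 200. A reader might infer that the trial is likely to report the wrong sign; the documents give no cost figures to support that.

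A third reply is that the fix rescues little power. This stands too: *no difference shown* would usually be the result either way. The gain is that the estimate and interval address the right quantity.

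**Conclusion.** The concern holds in a limited form. As written, the rule would very probably apply a rank test to total direct cost, and that test does not address the mean cost difference which the secondary objective in 3.2 and the end point in 7.4 require. That conclusion needs only the expectation that costs are skewed.

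The consequence rests on assumed costs. It ranges from frequent reversal (about 92% of trials with the supplement costed at 100 and a routine-cost SD of 100), through occasional reversal (4.5% at SD 600), to practically none with low sensitivity to a real saving (supplement not costed). No single figure in that range can be taken as the expected one. The primary incrustation score and the sample size are untouched. Severity: minor.

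**What to change.** Add to section 8.2:

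*Costs are compared as the difference in arithmetic means between arms with a bootstrap 95% confidence interval, whatever their distribution; the normality rule does not apply to costs.*

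Use the same mean difference, bootstrapped jointly with the difference in effect, for the cost-effectiveness end point.

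The change costs one sentence and a bootstrap run. It needs no new data and leaves the other analyses as they are. Its downside is a wide interval that will usually be inconclusive at this sample size, and the report should say so rather than read it as evidence of equal cost.
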